10.3 Study Period II (Track A – Bellafill Treatment)

10.3.1 Visit 5a (M1 ± 1W)

The following activities will be conducted 1M from Visit 4:

- UPT (if applicable)
- Concomitant Medication/Procedures and AE assessment

Touch-up Study Treatment

- The Investigator will examine the subject and determine if touch-up treatment is required to achieve optimal correction. Previously treated scars determined to be undercorrected will receive touch-up treatment. New scars (i.e., previously untreated) may not be treated.
- Document the number of scars treated as well as the method and volume of treatment.
- Subjects who merit additional treatment but decline touch-up treatment will not be retreated but will continue to participate in the study if they otherwise consent to continued participation.

10.3.2 Visit 6a (M3 ± 1W)

The following activities will be conducted 3M from Visit 4:

- Concomitant Medication/Procedures and AE assessment
- ASAS and PGAIS
 - The Investigator will refer to Baseline photographs for PGAIS evaluation.

10.3.3 Visit 7a (M6 ± 1W)

The following activities will be conducted 6M from Visit 4:

- Concomitant Medication/Procedures and AE assessment
- Facial Scar Photography
- ASAS and PGAIS
 - The Investigator will refer to Baseline photographs for PGAIS evaluation.
- QoL Scar Impact Scale and SGAIS
 - The subject will refer to Baseline photographs for SGAIS evaluation.
- Study Exit

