10.1 Assessment Schedule

								Pe	riod II	
Period I			Track A Bellafill			Track B No-Tx				
	Visit	Screening	1	2	3	4	5a	6a	7a	5b
	1 week = 7D 1 month = 28D	W -4	D0	W3 ±3D	W6 ±3D	W12 ±1W	M1 ±1W	M3 [†] ±1W	M6 [†] ±1W	M3 ^{††} ±1W
Inf	ormed Consent	Х								
Inc	l/Excl Criteria, Med Hx	Х	X confirm							
UF	PT (if applicable)	Х	X ¹			X ¹	X ¹			
Fa	cial Scar Photography	Х				X ¹			Х	Х
Ве	llafill Skin Test	X Placement	X Reading							
Microneedling Treatment			Х	Χ	Х					
Ra	ndomization					R				
Bellafill Injections Initial injection Touch-up						l²	T ³			
ş	ASAS (Investigator)	Х						Χ	Х	Χ
nen	PGAIS (Investigator)					X ¹		Х	Х	Х
PGAIS (Investigator) SGAIS (subject) QoL Scar Impact Scale						X ¹		Χ	X	Χ
Ass	QoL Scar Impact Scale (subject)		X ¹						Х	Х
Со	n Meds/Procedures	X	Χ	Χ	Χ	Х	Χ	Χ	Х	Χ
Ad	verse Events	Х	Х	Χ	Χ	Χ	Χ	Χ	Χ	Х

[†] Visits to occur 3M and 6M after last injection of Bellafill (i.e., initial treatment or touch-up treatment)

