10.2.2 Visit 1: Treatment Visit (D0)

The following activities will be conducted:

- Inclusion/Exclusion Criteria (confirmation)
- UPT (if applicable)
- Review skin test results and inclusion/exclusion criteria to confirm eligibility
- QoL Scar Impact Scale
 - Performed by the subject prior to receiving microneedling treatment.
- Microneedling treatment (see Section 5.1)
- Concomitant Medication/Procedures and AE assessment
- Provide HSV Prophylaxis with Acyclovir for subjects with a medical history of cold sores (may be provided prior to Visit 1 at the discretion of the Investigator).

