10.2.4 Visit 4 (W12 ± 1W)

The following activities will be conducted:

- Concomitant Medication/Procedures and AE assessment
- UPT (if applicable)
- PGAIS
 - The Investigator will refer to Baseline photographs for PGAIS evaluation.
- SGAIS
 - The subject will refer to Baseline photographs for SGAIS evaluation.
- Facial Scar Photography
- Randomization
 - Subject allocated to Track A (Bellafill Treatment) or Track B (No Treatment) as per Section 7.4.
- Bellafill injections Subjects randomized to Track A only
 - Document the number of scars treated as well as the method and volume of treatment.
- Scheduling of next clinic visit
 - Track A: Subjects randomized to Bellafill Treatment attend Visit 5a at 1 Month from this visit.
 - Track B: Subjects randomized to **No Treatment** attend Visit 5b at 24 Weeks from Visit 1 (i.e., approximately 3 Months from this Visit 4).

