10.4 Study Period II (Track B – No Treatment)

10.4.1 Visit 5b (M3 ± 1W)

The following activities will be conducted 24W from Visit 1:

- Concomitant Medication/Procedures and AE assessment
- Facial Scar Photography
- ASAS and PGAIS
 - The Investigator will refer to Baseline photographs for PGAIS evaluation.
- QoL Scar Impact Scale and SGAIS
 - The subject will refer to Baseline photographs for SGAIS evaluation.
- Study Exit

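### After randomisation, QoL is measured only at Month 6 in Track A and only at about Month 3 in Track B, so no time-matched between-track QoL comparison is possible

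*Combined protocol and SAP*

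**What the plan says.** Section 8 and the synopsis list four effectiveness measures: ASAS, PGAIS, SGAIS and the 33-item QoL scale. The schedule in section 10.1 and the visit lists in sections 10.2 to 10.4 agree on when QoL is taken:

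- **Visit 1 (Day 0), all subjects.** Section 10.2.2: "Performed by the subject prior to receiving microneedling treatment".
- **Visit 4 (randomisation).** No QoL. Section 10.2.4 lists PGAIS and SGAIS ("The subject will refer to Baseline photographs for SGAIS evaluation") but not this scale.
- **Visit 6a, Track A.** No QoL. Section 10.3.2 says "The following activities will be conducted 3M from Visit 4" and lists "ASAS and PGAIS" as the only scales.
- **Visit 7a, Track A.** QoL taken. Section 10.3.3: "The following activities will be conducted 6M from Visit 4".
- **Visit 5b, Track B, study exit.** Section 10.4.1 says "The following activities will be conducted 24W from Visit 1" and lists "QoL Scar Impact Scale and SGAIS".

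The protocol gives two anchors for 6a and 7a. Sections 10.3.2 and 10.3.3 count from Visit 4. The synopsis, section 3, the section 3.1 schematic note and the section 10.1 footnote count from the last Bellafill injection, which may be the Month 1 touch-up.

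Section 3 presents the trial as microneedling alone against microneedling followed by Bellafill. Section 12.2 plans exploratory comparisons between treatment groups at the 0.05 level without naming a scale or a visit.

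**The concern.** The tracks are randomised at Visit 4, so a sound comparison needs both measured at about the same time after Visit 4. For QoL the only contrast the schedule offers after randomisation is 7a in Track A against 5b in Track B. That contrast differs in treatment and also in time since randomisation, time since microneedling and time since the QoL baseline.

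Modelling cannot repair this. Track A has no scheduled QoL between Visit 1 and 7a, and Track B has none after 5b. Time and track do not overlap after randomisation, so any adjustment would rest on an assumed time course that the documents do not supply. Change from Visit 1 within each track can still be summarised, but it is not a randomised comparison.

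**Working it through.** **Inputs, all from the protocol**

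- 1 month = 28 days, so 4 weeks (section 10.1)
- Visit 4: 12 ± 1 weeks from Visit 1 (section 10.2.4)
- Visit 5a, the touch-up visit: 4 ± 1 weeks from Visit 4 (section 10.3.1)
- Visit 7a: 6 months = 24 ± 1 weeks, from Visit 4 or from the last injection, depending on the section
- Visit 5b: 24 ± 1 weeks from Visit 1 (section 10.4.1)

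Windows are applied around the actual date of the anchor visit.

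**The protocol's own figure.** Visit 5b is described as about 3 months after Visit 4. Check: 24 − 12 = 12 weeks, and 3 × 28 / 7 = 12 weeks. It reproduces.

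**Weeks from Visit 4 to the QoL assessment**

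- Track B, 5b: 24 − 12 = 12. Limits: 23 − 13 = 10 and 25 − 11 = 14.
- Track A, 7a counted from Visit 4, or no touch-up: 24. Limits: 23 and 25.
- Track A, 7a counted from a touch-up: 4 + 24 = 28. Limits: 3 + 23 = 26 and 5 + 25 = 30.

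**Gap between tracks, 7a minus 5b**

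- Without a touch-up, or from Visit 4: 24 − 12 = 12 weeks. Limits: 23 − 14 = 9 and 25 − 10 = 15.
- From a touch-up: 28 − 12 = 16 weeks. Limits: 26 − 14 = 12 and 30 − 10 = 20.

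The ranges 10–14 and 23–25 (or 26–30) do not overlap under either anchor.

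**Weeks from the only QoL baseline, Visit 1**

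- Track A: 12 + 24 = 36 (11 + 23 = 34 to 13 + 25 = 38), or 12 + 4 + 24 = 40 (11 + 3 + 23 = 37 to 13 + 5 + 25 = 43).
- Track B: 24 (23 to 25).
- Ratio of nominal intervals: 36 / 24 = 1.5, or 40 / 24 = 1.67.

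**If QoL were also taken at 6a (3 months = 12 ± 1 weeks)**

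- 6a counted from Visit 4, or no touch-up: 12 weeks (11 to 13). Gap to 5b: 0 weeks (11 − 14 = −3 to 13 − 10 = 3).
- 6a counted from a touch-up: 4 + 12 = 16 weeks (3 + 11 = 14 to 5 + 13 = 18). Gap to 5b: 4 weeks (14 − 14 = 0 to 18 − 10 = 8).

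**The case against.** The best defence is that the trial is a pilot with no formal sample size, that its inferential analyses are exploratory, and that section 12.2 never specifies a between-track QoL test. The objective in section 2 is to evaluate the sequential treatment, and within-track change from Visit 1 serves that. Taking QoL at each track's exit visit is a coherent choice. The loss is confined to one scale: ASAS and PGAIS are scheduled at both 6a and 5b in the table and in the visit text, and SGAIS is marked at both in the table.

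Most of this is true and limits the weight of the point. Because the direction of the bias is unknown, a 7a versus 5b test should be called confounded with follow-up time, not shown to be wrong in a given direction. But section 3 does frame a comparison of the two regimens, and section 12.2 does not exclude QoL from its group comparisons. That the other three scales have a Month 3 visit in both tracks shows that the structure for a matched comparison already exists and that QoL alone was left out of it.

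Two smaller points also stand. The 9-week minimum applies to in-window visits only: section 10.6 lets an unscheduled visit replace a missed one, and section 10.7 encourages final procedures at withdrawal, so some QoL forms may fall at other times. Such forms would not make a scheduled randomised comparison. And adding 6a does not give an exact match for touched-up subjects if timing runs from the last injection.

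**Conclusion.** The concern holds. As scheduled, QoL has no time-matched comparison between tracks after randomisation. Track A is assessed nominally 12 or 16 weeks later than Track B, with a range of 9 to 20 weeks across both anchors and all visit windows. This rests only on the protocol's own visit times, with no outside figures, and it is true whichever anchor for 7a is meant. The size and direction of the resulting bias cannot be derived, because the documents give no time course for the scale. It should be fixed: it affects one exploratory measure in a pilot, but nothing done at analysis can recover the comparison.

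**What to change.** 1. Add the QoL scale at Visit 6a in sections 10.1 and 10.3.2.
2. State in section 12.2 that between-track comparisons of QoL and the other scales use 6a against 5b, and that 7a is a within-Track-A summary of durability.
3. Reconcile the anchor for 6a and 7a across the synopsis, section 3, section 3.1, section 10.1, section 10.3.2 and section 10.3.3. How close the 6a to 5b match is depends on this.
4. Report actual days from Visit 4 to the compared visit, by track.
5. As a related but separate correction, list SGAIS in section 10.3.2, since section 10.1 already marks it at 6a.

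If QoL is not added at 6a, section 12.2 should say that it is summarised within track only. That needs text alone and prevents a time-confounded test, but it gives up the randomised QoL comparison.

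The cost is one 33-item self-completed form at an existing Track A visit (a few minutes of subject time), the matching eCRF page, the text edits, and the sponsor and IRB approval that section 13.2 requires for a protocol change. Two limits remain. The result is still open-label self-report against no treatment. And if timing from the last injection is kept, a touched-up subject's 6a falls nominally 4 weeks (0 to 8) later after Visit 4 than 5b does.

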10.4 Study Period II (Track B – No Treatment)

10.4.1 Visit 5b (M3 ± 1W)

The following activities will be conducted 24W from Visit 1:

- Concomitant Medication/Procedures and AE assessment
- Facial Scar Photography
- ASAS and PGAIS
 - The Investigator will refer to Baseline photographs for PGAIS evaluation.
- QoL Scar Impact Scale and SGAIS
 - The subject will refer to Baseline photographs for SGAIS evaluation.
- Study Exit

10.5 Instructions for Subjects

Prior to attending all study visits, subjects must refrain from applying facial cosmetics. Makeup may be re-applied after the study visits at the discretion of the Investigator. Subjects must avoid prolonged sun exposure to face for 24 hours prior to treatment.

Subjects should avoid strenuous exercise, NSAID products, consumption of alcoholic beverages and any exposure to sun or heat for at least 24 hours after treatment to reduce the risk of post treatment redness, swelling, and/or itching. Subjects should avoid applying sunscreen to the face for the first 24 hours following microneedling

treatment. After that period, sunscreen (UVB 30 minimum) should then be diligently applied. Subjects will also be advised not to manipulate or massage injected areas.

Subjects will be instructed to contact the Investigator or his/her research staff to report any unexpected symptoms or to ask any questions about the study.

10.6 Unscheduled Visits

Each time the subject returns to the study site the Investigator will solicit and record information about AEs, and concomitant medications, therapies and treatments. An interim or unscheduled visit may replace a scheduled visit if it occurs within the acceptable time window for a scheduled visit or if the scheduled visit was missed. All applicable procedures should be performed.

10.7 Early Discontinuation/Withdrawal

It is the right and duty of the Investigator to discontinue a subject's participation when the subject's health or well-being is threatened by continuation in the study. Such subjects should be withdrawn from the study and not continued under a modified regimen. In the event of premature discontinuation, the Investigator should determine the primary reason for discontinuation. A subject who is withdrawn from the study prior to initiation of treatment may be replaced. The following are circumstances that may result in the subject's discontinuation from the study:

- the subject experiences a serious AE rendering them unable to continue study participation; or
- the subject is unable to physically or mentally tolerate the test treatment; or
- the subject voluntarily withdraws; or
- the subject receives a prohibited therapy that could significantly confound the results.

Subjects may voluntarily withdraw from the study at any time without jeopardy to future medical care. They may also be administratively withdrawn if they fail to return for follow-up. If a subject chooses to withdraw from the study, the subject will be encouraged to have a final assessment and undergo the final procedures listed in the protocol.

For any subject who withdraws from the study the date and reason for withdrawal will be recorded on the eCRF. If an AE is ongoing at the time of the withdrawal, the Investigator will attempt to follow the subject until the AE has resolved or stabilized or until follow-up is no longer possible.

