10.9 Study Termination

The Sponsor reserves the right to terminate this study for any reason upon reasonable notice to the Investigators.

If conditions arise during the study that indicate that the study or an investigational site should be terminated, the Sponsor, Investigator, Monitor, IRB, and/or regulatory agencies will discuss the situation and take appropriate action after consultation.

Conditions warranting termination of the study or site include, but are not limited to:

- The discovery of an unexpected, serious, or unacceptable risk to subjects enrolled in the study;
- The decision on the part of the Sponsor to suspend or discontinue testing, evaluation, or development of the study device;
- Failure of the Investigator to comply with pertinent national or state regulations, IRB-imposed conditions, or protocol requirements;
- Submission of knowingly false information from the Investigator to the Sponsor, Monitor, IRB, or any regulatory agency.

11. Adverse Events

Throughout the course of the study, all AEs will be monitored and reported through the AE eCRF. If an AE occurs, the first concern will be the safety of the study subjects. All AEs occurring after study device administration will be followed until the event has resolved or stabilized or until follow-up is no longer possible.

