- A Bellafill Skin Test must be administered and evaluated prior to injection of Bellafill. Patients demonstrating a positive Skin Test or 2 equivocal Skin Tests should not be considered candidates for treatment. Patients demonstrating an anti-bovine collagen serum IgG level outside of the normal range at baseline also should not be considered candidates for treatment. Refer to the Bellafill Skin Test Instructions for Use.
- Use of Bellafill at specific sites in which an active inflammatory process (skin eruptions such as cysts, pimples rashes, or hives) or infection is present should be deferred until the inflammatory process has been controlled.
- Introduction of product into the vasculature may lead to embolization, occlusion of the vessels, ischemia, or infarction. Take extra care when injecting soft tissue fillers, for example inject the product slowly and apply the least amount of pressure necessary. Rare but serious adverse events associated with the intravascular injection of soft tissue fillers in the face have been reported and include temporary or permanent vision impairment, blindness, cerebral ischemia or cerebral hemorrhage, leading to stroke, skin necrosis, and damage to underlying facial structures. Immediately stop the injection if a patient exhibits any of the following symptoms, including changes in vision, signs of a stroke, blanching of the skin, or unusual pain during or shortly after the procedure. Patients should receive prompt medical attention and possibly evaluation by an appropriate health care practitioner specialist should an intravascular injection occur.

PRECAUTIONS

- Bellafill contains non-absorbable PMMA microspheres. Implantation is permanent and will not be reversed without physical removal.
- The safety of Bellafill for use during pregnancy and in breastfeeding females has not been established.
- Bellafill is packaged in a sealed tray containing individual treatment syringes with sterile needles for single patient use, packaged in a box. The tip of the syringe is sealed with a tamper-evident cover. Do not use if the seal on the tray lid or syringe is broken or removed. Do Not Resterilize.
- The safety of injecting greater amounts than 3.5 cc per treatment site or 8.9 cc overall has not been established.
- The safety and effectiveness of Bellafill for the treatment of non-distensible atrophic acne scars has not been established. The use of Bellafill for ice pick or sinus tract scars has not been studied.

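### Section 10.7 takes a subject withdrawn on health grounds out of the whole study, with no plan for AEs that begin afterwards or for the remaining assessments

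*Combined protocol and SAP*

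**What the plan says.** All references are to the combined protocol and SAP.

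- **Trigger and scope (10.7).** The investigator discontinues participation "when the subject's health or well-being is threatened by continuation in the study". The next sentence reads: "Such subjects should be withdrawn from the study and not continued under a modified regimen". A serious AE and inability to tolerate treatment are listed among the circumstances that may lead to discontinuation.
- **Ongoing AEs (10.7 and 11).** "If an AE is ongoing at the time of the withdrawal, the Investigator will attempt to follow the subject until the AE has resolved"; stabilisation, or follow-up becoming impossible, also ends this duty. The opening of Section 11 states the general rule: "All AEs occurring after study device administration will be followed until the event has resolved or stabilized or until follow-up is no longer possible".
- **Final assessment (10.7).** "If a subject chooses to withdraw from the study, the subject will be encouraged to have a final assessment and undergo the final procedures".
- **Off treatment but on study (10.3.1).** Subjects who merit a touch-up at Visit 5a but decline it "will not be retreated but will continue to participate in the study if they otherwise consent to continued participation".
- **How AEs are found (9 and 10.6).** They are solicited at post-treatment visits, phone calls or emails, and whenever the subject returns to the site.
- **Analysis (12.2 and 12.3).** The ITT set is everyone who passed screening and received the first microneedling treatment. Missing data are not imputed. Section 12.3 tabulates AE incidence and severity and lists all reports.
- **The implant (Appendix 4, Precautions).** "Implantation is permanent and will not be reversed without physical removal".

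**The concern.** Whether a subject should have more study treatment and whether the subject should still be observed are separate questions. Section 10.7 answers both with one act. From Visit 5a onwards in Track A, and from Visit 4 onwards in Track B, the schedule in 10.1 contains no further study treatment, so a withdrawal after that point removes only observation. In Track A the implant stays in place.

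Safety is part of the single study objective (Section 2). Subjects withdrawn on health grounds are a selected group, so the loss of their later data may well be related to outcome. At stake are the detection of second or later AEs in those subjects and the completeness of an analysis that is described as ITT.

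**Working it through.** The plan gives no figure to reproduce on this point. The check is mainly a comparison of passages, followed by arithmetic for scale.

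**Step 1: what each route out of treatment keeps**

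| Item | Declines touch-up (10.3.1) | Chooses to leave (10.7) | Withdrawn by investigator on health grounds (10.7) |
|---|---|---|---|
| AE ongoing at that time | followed | followed | followed |
| AE beginning later | sought at scheduled visits | no contact planned | no contact planned |
| Final assessment | scheduled Visit 7a | encouraged | not mentioned |
| Remaining scheduled visits | kept | not kept | not kept |

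The Section 11 rule applies to an AE once it is known. It does not create a contact at which a new or recurrent AE would be found. Sections 9 and 10.6 tie detection to contact, and none is scheduled after withdrawal once the ongoing AE has settled.

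**Step 2: length of the unobserved period**

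Section 10.1 sets 1 month = 28 days. Planned Track A follow-up for a subject without touch-up is 6 × 28 / 7 = 24 weeks after injection. A withdrawal at Month 1 (week 4) leaves 24 − 4 = 20 weeks without planned AE contact, apart from follow-up of an AE already open.

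**Step 3: efficacy data lost**

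By Sections 10.3.2, 10.3.3 and 10.4.1, the lost items are at least ASAS and PGAIS at 6a, and photography, ASAS, PGAIS, SGAIS and the QoL scale at 7a (Track A) or 5b (Track B). With 45 subjects allocated 1:1, each track has 45 / 2 = 22.5, so about 22 or 23 if all reach Visit 4. Each withdrawal removes one subject from the later summaries of a group that size, and Section 12.2 puts nothing in its place.

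**Step 4: order of magnitude for late-onset AEs**

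Inputs from Appendix 4 (nasolabial-fold studies):
- AEs with onset 3 months or more after treatment: 6+3+2+2+1+1+1+1+1 = 18 events in 391 subjects.
- Follow-up from the Table 1 footnotes: 285 subjects for 12 months and 106 for 6 months.

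Assuming complete follow-up and a constant rate after Month 3:
- Time at risk after Month 3: 285 × 9 + 106 × 3 = 2,883 subject-months.
- Rate: 18 / 2,883 = 0.00624 per month.
- Months 3 to 6: 0.00624 × 3 = 0.0187, or about 1.9 events per 100 subjects.

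The plan states no withdrawal rate. For an assumed number of early withdrawals in Track A:

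| Withdrawn (assumed) | Expected events, Months 3–6 |
|---|---|
| 1 | 0.02 |
| 2 | 0.04 |
| 3 | 0.06 |
| 4 | 0.07 |

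These figures come from another indication and from unselected subjects. They leave out events beginning between withdrawal and Month 3, and they count events, not subjects. They show scale only and do not predict this trial.

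**Step 5: granulomas**

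In Appendix 4, Table 9, 1 of 17 granulomas among 1,008 subjects began within 6 months. For 22 to 23 subjects that gives 22/1,008 to 23/1,008, about 0.02 expected within the planned follow-up. Most would begin after study exit whatever the withdrawal rule.

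**The case against.** The strongest defence is that the protocol already protects these subjects, and much of it stands.

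- **The event behind the withdrawal is followed.** A reader might infer that withdrawn subjects lose all AE follow-up. Sections 10.7 and 11 say otherwise.
- **Withdrawal is not automatic.** It rests on the investigator's judgement that continuing is a threat. Once only observation remains, that will seldom be so. A subject who reacted can also attend Visit 5a, receive no touch-up and stay in the study, so 10.3.1 and 10.7 do not contradict each other.
- **Subject-level AE incidence is not shown to be biased.** A reader might infer that Track A would look too safe. A subject withdrawn for an AE is already a case in 12.3. Only later or second events could be missed, which affects event counts and the incidence of event types the subject had not yet had.
- **No text removes these subjects from the safety denominator.** Section 12.3 states no such exclusion, and the no-imputation sentence stands under efficacy in 12.2. One subject in 22 is 4.5% of a track, but that is a weight and shows no bias.
- **Two Appendix 4 figures do not measure the gap.** In Table 8, (37+53+32)/177 = 69% of device-related AEs lasted more than 30 days or were ongoing. Those are durations of known AEs, which would be followed anyway. The crude 18/391 = 4.6 per 100 covers longer follow-up than this study has after Month 3.

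What the defence does not supply is any passage that plans contact for AEs beginning after withdrawal, keeps the remaining assessments, or offers a final assessment to a subject the investigator withdraws.

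**Conclusion.** The point holds in a limited form. Section 10.7 follows what is open on the day of withdrawal and plans nothing after it: no search for new or recurrent AEs, no retained assessments and, for investigator-initiated withdrawals, no final assessment. These subjects remain in the ITT set of 12.2 without contributing later efficacy data.

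For one subject the loss can be as long as 20 of 24 weeks. For the study the size is unknown, because no withdrawal rate is given, and few subjects are likely to be affected. The conclusion rests on reading 10.7 as withdrawal from all study participation, as its wording says, and on the absence of any other passage that schedules contact after it. It is a cheap improvement to an exploratory pilot and does not invalidate the design.

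**What to change.** Leave the decision on further study treatment exactly as the protocol has it, and change only what is observed afterwards.

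1. In 10.7, separate stopping study treatment from leaving the study. A subject who has received microneedling or Bellafill stays on the existing visit schedule, with at least AE contact by visit or phone, to the 7a or 5b date, unless consent to follow-up is withdrawn. A subject withdrawn before randomisation has no track, so the text should name a date; the 5b date is already counted from Visit 1.
2. Extend the encouragement of a final assessment to subjects withdrawn by the investigator.
3. Record treatment stopped and left study as separate eCRF items, each with date and reason.

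The cost is a few sentences in 10.7, a small eCRF addition, and a few remaining visits or calls for subjects who would otherwise have exited. The visits are already in the schedule.
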